2.2 Study Design Overview

[figure not shown]
The schematic of the study is shown in Figure 1.

Figure 1. Study Schematic**2.3****Treatment Assignment and Blinding**

Subjects will be randomized in a 2:2:2:1 ratio to receive OnabotA X [REDACTED] [REDACTED] or [REDACTED] placebo [REDACTED]. Randomization will be stratified at each investigator site by baseline investigator-rated AGLSS at maximum contraction, using central by block stratified randomization. The same block will not be shared across investigative sites or by baseline GL severity assessment. AbbVie will provide instructions for [REDACTED] preparations and treatment administration separately, in the pharmacy manual.

2.4**Sample Size Determination**

The sample size was chosen empirically. [REDACTED]
[REDACTED]
[REDACTED]
[REDACTED]

3.0 Endpoints

3.1 Primary Endpoint(s)

The primary efficacy endpoint is achievement of \geq 1-grade improvement from baseline on the Allergan Glabellar Line Severity Scale (AGLSS) according to investigator assessments at maximum contraction at Day 30.

3.2 Secondary Endpoint(s)

- Achievement of None or Mild on the investigator-rated AGLSS assessments at maximum contraction at Day 30;

3.3 Other Efficacy Endpoint(s)

A series of 14 horizontal black bars of varying lengths, decreasing in size from top to bottom. The bars are set against a white background.

A series of nine horizontal black bars of varying lengths, decreasing from left to right. The bars are positioned at different vertical intervals, creating a stepped effect. The first bar is the longest and is positioned at the top. Subsequent bars are progressively shorter and are positioned lower down, with the ninth bar being the shortest and positioned at the bottom. The bars are set against a white background.

3.4 Safety Endpoint(s)

The safety endpoints for this study include:

- Adverse Events
- Abbreviated Physical Examination (general appearance, head, ears, eyes, nose, throat, and neck)

- Clinical Laboratory Test [REDACTED]
- Vital Sign Measurements [REDACTED]
[REDACTED]
- Electrocardiogram [REDACTED]
[REDACTED]
- Neurologic Assessment

3.5 Additional Endpoint(s)

[REDACTED]

[REDACTED]

[REDACTED]

[REDACTED]

[REDACTED]

[REDACTED]

4.0 Analysis Populations

The following population sets will be used for the analyses.

The Intent to Treat (ITT) Population includes all randomized subjects. The ITT Population will be used for all efficacy analyses. [REDACTED]

[REDACTED]

The Safety Analysis Set consists of all subjects who received at least 1 dose of study drug. The safety analyses will be based on the safety population. [REDACTED]

[REDACTED]

5.0 Subject Disposition

The total number of subjects who were screened, enrolled, and treated will be summarized. Reasons for exclusion, including screen failure, will be summarized.

For end of study participation, the number and percentage of subjects who completed the protocol defined follow-up period (or did not with associated reasons) will be summarized overall and by treatment group.

6.0 Study Drug Duration and Compliance

Duration of exposure will be summarized with descriptive statistics (mean and standard deviation, median, Q1, Q3, minimum, and maximum). The number of subjects exposed for specific period of time

will also be summarized. Duration of exposure will be calculated as date of study exit minus date of study drug administration +1.

7.0 Demographics, Baseline Characteristics, Medical History, and Prior/Concomitant Medications

Demographics, baseline characteristics, medical history, prior and concomitant medications, and concurrent procedure will be summarized overall and by treatment group for the ITT Population.

[REDACTED]

[REDACTED]

[REDACTED]

[REDACTED]

7.1 Demographics and Baseline Characteristics

Continuous demographic variables include age. Categorical demographic variables include sex, ethnicity, race, age group [REDACTED].

Baseline characteristics include weight, height, body mass index (BMI), Fitzpatrick skin type, investigator-rated and subject-rated AGLSS severity at maximum contraction and at rest, baseline Facial Line Satisfaction Questionnaire (FLSQ[©]) impact domain score,

[REDACTED]

[REDACTED]

[REDACTED]

7.2 Medical History

Medical history data will be coded using the Medical Dictionary for Regulatory Activities (MedDRA). [REDACTED]

[REDACTED]

[REDACTED]

[REDACTED]

[REDACTED]

[REDACTED]

[REDACTED]

7.3 Prior and Concomitant Medications

Prior and concomitant medications will be summarized by generic name. [REDACTED]

[REDACTED]

[REDACTED]

[REDACTED]

[REDACTED] The number and percentage of subjects taking medications will be summarized by generic drug name based on the World Health Organization (WHO) Drug Dictionary for both prior and concomitant medications.

7.4 Concurrent Procedure

All procedures undergone on or after Study Day 1 visit through the exit visit will be considered concurrent procedures. Concurrent procedure will be summarized by MedDRA high level term and preferred term. [REDACTED]

[REDACTED]

[REDACTED]

8.0 Handling of Potential Intercurrent Events for the Primary and Key Secondary Endpoints

The primary endpoint and secondary endpoints will be analyzed based on the ITT population, [REDACTED]

- Subjects who are missing data for any other reason for the endpoint will count as though they hypothetically continued in the study.

9.0 Efficacy Analyses

9.1 General Considerations

All efficacy analyses will be conducted in the ITT Population in each period. [REDACTED]

[REDACTED]

[REDACTED]

[REDACTED]

[REDACTED]

[REDACTED] All efficacy results will be summarized by treatment group.

Unless otherwise specified, any subject who is randomized based on a wrong stratum will be analyzed according to the actual stratum the subject belongs to.

"Baseline" refers to the last non-missing observation before the first administration of study drug or randomization if no study drug is given.

9.2 Handling of Missing Data

Missing data will be imputed using multiple imputation (MI) method for the primary and secondary endpoints.

[REDACTED]

[figure not shown]
[REDACTED]

[REDACTED]

[REDACTED]

[REDACTED]

[REDACTED]

Each of the 5 imputation data sets will be analyzed individually, then combined to generate the final inferences as described in Section 9.3.2.

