4 INVESTIGATIONAL PLAN

4.1 Overall Study Design and Plan

This is a double-blind, randomized, placebo-controlled, Phase 2 study to assess the safety and efficacy of OnabotA X for the treatment of moderate to severe GL. To be eligible for enrollment, at baseline subjects must have AGLSS scores of moderate or severe GL at maximum contraction (also called frown or furrow) by investigator and subject assessments.

Approximately 280 subjects will be enrolled at approximately 18 sites. Eligible subjects will be randomized in a 2:2:2:1 ratio to receive OnabotA X [REDACTED] or [REDACTED] placebo. Randomization will be stratified at each investigator site by the investigator-assessed baseline severity of GL (AGLSS score) at maximum contraction. Overall study enrollment will be monitored to achieve an approximately balanced [REDACTED] distribution of subjects with investigator-assessed moderate or severe GL at maximum contraction at baseline.

Safety parameters [REDACTED]

[REDACTED] will be monitored (see Operations Manual [[Appendix F](#)] Section 3). At [REDACTED] females of childbearing potential will undergo pregnancy testing. For all subjects, AEs will be collected, whether solicited or spontaneously reported by the subject. Blood samples for immunogenicity testing will be collected [REDACTED]

[figure not shown]
Efficacy will be evaluated based on AGLSS assessed by the investigator and subject, and based on subject responses to FLSQ, [REDACTED]

[REDACTED] Standardized facial photography will be collected at all study visits from Day 1 through study exit.

The schematic of the study is shown in [Figure 1](#). Further details regarding study procedures are in the Operations Manual.

See [Section 5](#) for information regarding eligibility criteria.

Figure 1. Study Schematic

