7.3 Handling Potential Intercurrent Events for the Primary and Key Secondary Endpoints

Missing data will be imputed using multiple imputation (MI) method for the primary and secondary endpoints (see Section 3.2).

After imputation, the changes from baseline values will be calculated. The responder status based on raw values or change from baseline values will then be derived for each post baseline visit.

Each of the 5 imputation data sets will be analyzed individually.

To obtain pooled CMH p-value, the Wilson-Hilferty transformation will be used.

A sensitivity analysis will also be performed for the primary efficacy variable using observed data.

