7.8 Sample Size Determination

The sample size was chosen empirically. The primary efficacy parameter is the proportion of subjects with a ≥ 1 -grade improvement from baseline according to investigator-rated AGLSS at maximum contraction at Day 30. Based on previous BOTOX studies, the responder rate of ≥ 1 -grade improvement from baseline on the GL severity scale  Assuming  responder rate for OnabotA X and placebo, respectively, at least 28 OnabotA X and 14 placebo subjects will be required to detect the above intervention difference with a power of 90% or greater at the 2 sided 5% significance level for the primary endpoint.

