9.3.2 Main Analysis of Primary Efficacy Endpoint(s)

The attributes of the estimands corresponding to the primary efficacy endpoint are summarized in Table 1.

Table 1. Summary of the Estimand Attributes of the Primary Efficacy Endpoint

Estimand Label	Attributes of the Estimand				
	Treatment	Endpoint	Population	Handling of Intercurrent Events	Statistical Summary
Hypothetical estimand for primary endpoint	OnabotA X or placebo	Achievement of ≥ 1 -grade improvement from baseline on the AGLSS according to investigator assessments at maximum contraction at Day 30	ITT (All randomized)	Subjects who discontinue study prior to Day 30 assessments, or who do not have AGLSS assessments will be included in the analysis as a hypothetical scenario in which they had not missed the AGLSS assessments	Difference in response proportions between each active treatment group and placebo, after MI using CMH test stratified by baseline investigator-rated AGLSS at maximum contraction

AGLSS = Allergan Glabellar Line Severity Scale; CMH = Cochran-Mantel-Haenszel; ITT = intent-to-treat; MI = multiple imputation; OnabotA X = onabotulinumtoxinA X

The evaluation of the equality of the proportions of responders will be based on Cochran-Mantel-Haenszel (CMH) test stratified by baseline investigator-rated AGLSS at maximum contraction. Wald confidence intervals for proportions of responders and difference in the proportion of responders will be presented. The Breslow-Day homogeneity of the odds-

ratio test will be performed to test the treatment-by-investigator-rated baseline GL severity at maximum contraction interaction.

To obtain pooled CMH p-value, the Wilson-Hilferty transformation will be used.^{1,2}

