The key secondary efficacy endpoints are to be analyzed similarly to the primary endpoint using multiple imputation, as specified in Section 9.2. [REDACTED]

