13.0 Overall Type-I Error Control

Analyses will be conducted using a gated hierarchical testing procedure to preserve a familywise Type I error rate of $\alpha=0.05$ for each OnabotA X group compared to placebo, separately.

A horizontal bar chart consisting of four solid black bars of increasing length from left to right. The bars are separated by small gaps and are set against a white background.

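### Five imputations leave any key secondary p-value near 0.05 open to avoidable Monte Carlo noise; raising the number to at least 50 costs almost nothing

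*SAP*

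**What the plan says.** Both documents fix the number of imputations at 5. SAP section 9.2: "Each of the 5 imputation data sets will be analyzed individually, then combined to generate the final inferences as described in Section 9.3.2". Protocol section 7.3: "Each of the 5 imputation data sets will be analyzed individually".

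SAP section 9.3.2 gives the pooling rule: "To obtain pooled CMH p-value, the Wilson-Hilferty transformation will be used". SAP section 9.4.2 carries the approach over to the key secondaries: "The key secondary efficacy endpoints are to be analyzed similarly to the primary endpoint using multiple imputation, as specified in Section 9.2".

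SAP section 13.0 makes these p-values consequential: "Analyses will be conducted using a gated hierarchical testing procedure", at a familywise 0.05 for each dose against placebo separately. Because control is separate by dose, the hierarchy must run across endpoints. The order itself is redacted.

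The primary endpoint has an observed-data sensitivity analysis (SAP 9.3.3). For the key secondaries, SAP 9.4.3 plans none. Most of SAP 9.2 is redacted, so the imputation model and any prespecified seed cannot be seen.

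**The concern.** Multiple imputation uses random draws, so the pooled p-value depends on the seed. With many imputations this hardly matters. With 5, both the average of the transformed test statistics and the estimate of their spread vary noticeably from one seed to the next.

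A hierarchical procedure turns each p-value into a pass or fail at 0.05, and a fail closes the tests that follow it. Three key secondaries and three active groups give up to nine such decisions. The two FLSQ endpoints look the more exposed: one is read at Day 60, which leaves more time for dropout, and the other uses only subjects with a baseline score of at least 14. At stake is whether a borderline secondary verdict reflects the data or the draw of the imputations.

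**Working it through.** **Inputs from the documents**
- Total 280 (Protocol 4.1), allocated 2:2:2:1 (SAP 2.3). Each active group has 280 × 2/7 = 80 and placebo has 280 × 1/7 = 40, so each comparison is 80 v 40.
- Two-sided 5% level (Protocol 7.8); CMH test stratified by baseline severity, two strata (SAP 9.3.2); m = 5.

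**Assumptions, because the visible text gives no figure**
- Missing rates of 2%, 5%, 10% and 15%, missing at random (SAP 2.1 states that mechanism).
- Two equal strata and a placebo response of 30%.
- Missing responder status imputed as Bernoulli by arm and stratum, with the response probability drawn from its beta posterior.

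**Step 1: the plan's own figure.** Protocol 7.8 says that 28 active and 14 placebo subjects give at least 90% power. The responder rates are redacted, so this cannot be reproduced. It is compatible, without continuity correction, with placebo 5% v active 50% or more, 10% v 57.5% or more, or 20% v 70% or more. For 10% v 60%, power is 93% at 28 v 14 and 99.999% at 80 v 40. With effects of that size the primary p-value will not be near 0.05.

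**Step 2: pooling.** For each imputed set with CMH chi-square X (1 df), the Wilson-Hilferty transformation is

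W = (X^(1/3) − 7/9) / √(2/9).

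Over m sets with mean W̄ and between-set variance B, the total variance is T = 1 + (1 + 1/m)B. Then t = W̄/√T is referred to the upper tail of a t distribution with df = (m − 1)(1 + 1/r)², where r = (1 + 1/m)B. The upper tail of a transformed chi-square corresponds to the two-sided CMH test.

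**Step 3: vary only the seed.** Each scenario used 25 fixed data sets with 2,000 seeds each. The reference p is the same data set pooled over 3,000 imputations. A seed crosses if its p falls on the other side of 0.05 from the reference.

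Reference p between 0.045 and 0.055:

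| Missing | 95% range of p, m=5 | SD of p, m=5 / 50 / 100 | Seeds crossing, m=5 / 50 / 100 |
|---|---|---|---|
| 2% | 0.037–0.067 | 0.0079 / 0.0024 / 0.0017 | 41% / 24% / 20% |
| 5% | 0.033–0.077 | 0.0115 / 0.0034 / 0.0024 | 39% / 21% / 14% |
| 10% | 0.026–0.097 | 0.0184 / 0.0052 / 0.0037 | 46% / 34% / 29% |
| 15% | 0.021–0.125 | 0.0272 / 0.0075 / 0.0052 | 46% / 37% / 32% |

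Allowing for variation between simulations, the 5% row is best read as about 0.03 to 0.08–0.09. For an assumed 60 v 30 subset (FLSQ Impact), the m=5 range is 0.033–0.078 at 5% missing and 0.026–0.100 at 10%.

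Reference p further from 0.05, share of seeds crossing:

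| Missing | Ref p ≈ 0.032, m=5 | Ref p ≈ 0.032, m=50 or 100 | Ref p ≈ 0.022, m=5 |
|---|---|---|---|
| 2% | 1% | 0% | not run |
| 5% | 6% | 0% | 0% |
| 10% | 15% | 0% | 3% |
| 15% | 20% | 0% | 7% |

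A separate simulation of the 0.032 case gave about 1.5%, 5%, 17% and 19% with m=5, and 0% with m=100.

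**Step 4: gain from a larger m.** Theory suggests that noise falls with √m: √(50/5) = 3.2 and √(100/5) = 4.5. The simulated SDs at 5% missing agree: 0.0115/0.0034 = 3.4 and 0.0115/0.0024 = 4.8.

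**Step 5: how often p is near 0.05 at all.** The chance that a complete-data p falls in 0.03–0.07 at 80 v 40 is about 0.0001 for 10% v 60%, 6% for 20% v 50%, 15% for 20% v 40% and 14% for 30% v 50%.

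**The case against.** The best counter-argument is that the simulation overstates the noise. Protocol 7.3 derives change from baseline and responder status after imputation, so the underlying scores are what is imputed, and other visits may inform them. In a run at 5% missing with reference p about 0.05, an auxiliary measure correlated 0.8–0.9 with the outcome (an assumption) lowered the m=5 SD of p from about 0.0126 to about 0.008. That is about one third less noise, but not none. Missing data may also be few: treatment is a single Day 1 administration, the endpoints fall at Day 30 or 60, and Protocol 5.6 keeps subjects who stop treatment in follow-up. Both points stand, so the percentages above are conditional.

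Four stronger readings are tempting but unsupported.
- A reader might infer that the results cannot be reproduced because no seed is fixed. The seed may be in the redacted part of SAP 9.2. If so, the analysis reproduces exactly and no favourable seed can be chosen. The verdict would still depend on an arbitrary number, but the seed cannot be called missing.
- A reader might infer that the pooled test rests on 4 degrees of freedom. That is the figure for the between-imputation component. The median df of the pooled test at m=5 was about 1,250 at 5% missing and 240 at 10%. Simulated Type I error was 0.052–0.057, so the pooling method itself is acceptable.
- A reader might infer that noise on any key secondary blocks later tests. The order is redacted, and noise on the last endpoint in the sequence blocks nothing.
- A reader might infer that 100 imputations settle the matter. With reference p between 0.045 and 0.055, 14–32% of seeds still cross.

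**Conclusion.** The point holds in conditional form and is minor. If some data are missing and a key secondary p-value lies near 0.05, m=5 adds enough noise to change the verdict. The clearest evidence is the result with reference p about 0.032: it is not on the boundary, yet it would be lost in 1–20% of seeds across the missing rates examined, and in about 0% with m of 50 or 100.

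This rests on the assumed missing rates and on an imputation model without auxiliary information. The exposure is confined to moderate effects, roughly 20–30 percentage points. The visible text gives no expected rates for the key secondaries, so how likely such effects are cannot be judged. The documents do not support a claim that the primary endpoint is at risk: at the planned effect size its p-value will be far from 0.05.

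**What to change.** In SAP section 9.2 and Protocol section 7.3, replace 5 imputations with at least 50; 100 is just as easy. Confirm that the redacted text prespecifies the seed, and add it before unblinding only if it does not.

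The cost is one number in two places and seconds of computing time, with no change to the estimand, the imputation model, the test or study conduct. Protocol 8.1 sends every amendment to the ethics committee, so the protocol edit can wait for the next amendment, with the SAP recording the change meanwhile. Seed noise shrinks about three-fold at 50 and five-fold at 100; p-values very close to 0.05 will keep some seed dependence at any finite number.

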9.3 Primary Efficacy Endpoint(s) and Analyses

9.3.1 Primary Efficacy Endpoint(s)

The primary efficacy endpoint is achievement of ≥ 1 -grade improvement from baseline on the investigator-based AGLSS at maximum contraction at Day 30.

9.3.2 Main Analysis of Primary Efficacy Endpoint(s)

The attributes of the estimands corresponding to the primary efficacy endpoint are summarized in Table 1.

Table 1. Summary of the Estimand Attributes of the Primary Efficacy Endpoint

Estimand Label	Attributes of the Estimand				
	Treatment	Endpoint	Population	Handling of Intercurrent Events	Statistical Summary
Hypothetical estimand for primary endpoint	OnabotA X or placebo	Achievement of ≥ 1 -grade improvement from baseline on the AGLSS according to investigator assessments at maximum contraction at Day 30	ITT (All randomized)	Subjects who discontinue study prior to Day 30 assessments, or who do not have AGLSS assessments will be included in the analysis as a hypothetical scenario in which they had not missed the AGLSS assessments	Difference in response proportions between each active treatment group and placebo, after MI using CMH test stratified by baseline investigator-rated AGLSS at maximum contraction

AGLSS = Allergan Glabellar Line Severity Scale; CMH = Cochran-Mantel-Haenszel; ITT = intent-to-treat; MI = multiple imputation; OnabotA X = onabotulinumtoxinA X

The evaluation of the equality of the proportions of responders will be based on Cochran-Mantel-Haenszel (CMH) test stratified by baseline investigator-rated AGLSS at maximum contraction. Wald confidence intervals for proportions of responders and difference in the proportion of responders will be presented. The Breslow-Day homogeneity of the odds-

ratio test will be performed to test the treatment-by-investigator-rated baseline GL severity at maximum contraction interaction.

To obtain pooled CMH p-value, the Wilson-Hilferty transformation will be used.^{1,2}

9.3.3 Sensitivity and Supplementary Analyses of the Primary Efficacy Endpoint(s)

A sensitivity analysis will be performed for the primary efficacy variable using observed data.

9.4 Secondary Efficacy Endpoints and Analyses

9.4.1 Key Secondary Efficacy Endpoints

The key secondary endpoints, which utilize both the AGLSS and FLSQ, include:

- Achievement of None or Mild on the investigator-rated AGLSS assessments at maximum contraction at Day 30;
- Responses of Very satisfied or Mostly satisfied on satisfaction with treatment per the FLSQ follow-up version Item 5 at Day 60;
- Achievement of \geq 14-point psychosocial impact improvement from baseline at Day 30 per the FLSQ Impact domain, among subjects with baseline scores \geq 14 points

9.4.2**Main Analyses of Key Secondary Efficacy Endpoints**

The attributes of the estimands corresponding to the secondary efficacy endpoints are summarized in Table 2.

Table 2. Summary of the Estimand Attributes of the Secondary Efficacy Endpoints

Attributes of the Estimand					
Estimand Label	Treatment	Endpoint	Population	Handling of Intercurrent Events	Statistical Summary
Hypothetical estimand for secondary endpoint	OnabotA X or placebo	Achievement of None or Mild on the investigator-rated AGLSS assessments at maximum contraction at Day 30	ITT (All randomized)	Subjects who discontinue study prior to Day 30 assessments, or who do not have AGLSS assessments will be included in the analysis as a hypothetical scenario in which they had not missed the AGLSS assessments	Difference in response proportions between each active treatment group and placebo, after MI using CMH test stratified by baseline investigator-rated AGLSS at maximum contraction
		Responses of Very satisfied or Mostly satisfied on satisfaction with treatment per the FLSQ follow-up version Item 5 at Day 60		Subjects who discontinue study prior to Day 60 assessments, or who do not have FLSQ assessments will be included in the analysis as a hypothetical scenario in which they had not missed the FLSQ assessments	
		Achievement of ≥ 14 -point psychosocial impact improvement from baseline at Day 30 per the FLSQ Impact domain, among subjects with baseline scores ≥ 14 points		Subjects who discontinue study prior to Day 30 assessments, or who do not have FLSQ assessments will be included in the analysis as a hypothetical scenario in which they had not missed the FLSQ assessments	

AGLSS = Allergan Glabellar Line Severity Scale; CMH = Cochran-Mantel-Haenszel; ITT = intent-to-treat; MI = multiple imputation; OnabotA X = onabotulinumtoxinA X

The key secondary efficacy endpoints are to be analyzed similarly to the primary endpoint using multiple imputation, as specified in Section 9.2. [REDACTED]

